- ② BACKGROUND, RATIONALE & GOALS
- ③ RESEARCH PLAN
- ④ CONSENT PLAN
- ⑤ RISKS, PRIVACY & CONFIDENTIALITY
- ⑥ POPULATIONS WITH SPECIAL CONSIDERATIONS
- ⑦ INSTITUTIONAL REQUIREMENTS
- ⑧ DOCUMENTS

End of Application

Click Continue below to exit and submit this project

ID: HM20012696

View: Bio-Medical Project Drugs

Bio-Medical Project Drugs

1. * **Drug:**
Nicotine-containing electronic cigarette liquid (10 and 30 mg nicotine) in tobacco, menthol, dessert, and fruit flavors
2. * **Manufacturer:**
AVAIL Inc
3. * **Select all types that apply:**

FDA Approved and being used as approved

Marketed Drug/Biologic Exempt from IND

 Investigational Drug/Biologic/Supplement used as drug

 Supplement

 Over the Counter Medication

 Other (Drug or Compound Not Listed Above)

4. * Will the doses of drug administered and the dosing schedule match FDA approved labeling: (if not, include all doses and dosing schedules in the Methods)

 Yes

 No

 Not Applicable

5. * Select who holds the Investigational New Drug (IND) application for the drug/biologic:

 External to VCU Sponsor or Investigator

 VCU Sponsor-Investigator

 VCU Sponsor who is not the Investigator

 Not Required

6. Indicate the drug's IND number, if applicable. If the drug qualifies for IND exemption, enter "IND Exempt":

ID: HM20012696

View: Bio-Medical Project Drugs

Bio-Medical Project Drugs

1. * **Drug:**
Own brand cigarettes

2. * **Manufacturer:**
Various Manufacturers

3. * **Select all types that apply:**

 FDA Approved and being used as approved

 Marketed Drug/Biologic Exempt from IND

 Investigational Drug/Biologic/Supplement used as drug

 Supplement

 Over the Counter Medication

 Other (Drug or Compound Not Listed Above)

4. * Will the doses of drug administered and the dosing schedule match FDA approved labeling: (if not, include all doses and dosing schedules in the Methods)

Yes

No

Not Applicable

5. * Select who holds the Investigational New Drug (IND) application for the drug/biologic:

External to VCU Sponsor or Investigator

VCU Sponsor-Investigator

VCU Sponsor who is not the Investigator

Not Required

6. Indicate the drug's IND number, if applicable. If the drug qualifies for IND exemption, enter "IND Exempt":

ID: HM20012696

View: Bio-Medical Project Drugs

Bio-Medical Project Drugs

1. * Drug:

Own brand electronic cigarette liquid

2. * Manufacturer:

Various Manufacturers

3. * Select all types that apply:

FDA Approved and being used as approved

Marketed Drug/Biologic Exempt from IND

Investigational Drug/Biologic/Supplement used as drug

Supplement

Over the Counter Medication

Other (Drug or Compound Not Listed Above)

4. * Will the doses of drug administered and the dosing schedule match FDA approved labeling: (if not, include all doses and dosing schedules in the Methods)

Yes

No

Not Applicable

5. * Select who holds the Investigational New Drug (IND) application for the drug/biologic:

External to VCU Sponsor or Investigator

VCU Sponsor-Investigator

VCU Sponsor who is not the Investigator

Not Required

6. Indicate the drug's IND number, if applicable. If the drug qualifies for IND exemption, enter "IND Exempt":

ID: HM20012696

View: SF_IRB_ConsentPlan_Groups

Consent Groups

1. * Enter a descriptive name for this consent / assent group:
In-person consent

2. * Select all that apply to this consent / assent group:

Name

Written/Signed Consent by Participant

Written/Signed Consent by Parent/Guardian (for child) or Legally Authorized Representative (for adult)

Written/Signed Consent for Genetic Testing

Written/signed assent by Child or Decisionally Impaired Adult

Verbal Assent by Child

Short Form Consent (limited applicability)

None of the Above (select waiver below)

3. * Select any waivers that apply to this consent / assent group:

No Waivers Requested

Waiver of Some or All Elements of Consent

Waiver of Assent by Child or Decisionally Impaired Adult

Waiver of Parental Permission or Legally Authorized Representative Consent

Waiver of Documentation of Consent/Assent (not signed)

Exception from Informed Consent (for emergency research only)

4. * Select all study team role(s) that will obtain consent / assent from this group:

Principal Investigator

Co/Sub-Investigator

Medical or Psychological Responsible Investigator

Student Investigator

Research Coordinator

Research Nurse

Consultant

Research Assistant

Pharmacist

Statistician

Regulatory Coordinator

Trainee/Student (i.e. not Student-Investigator)

Other

N/A: Requesting Waiver of Consent

5. * **Describe the consent procedures used for this group. Include when, where, and how consent / assent will be obtained both initially and, if applicable, during ongoing participation in the study:**
In a private room located at the Center for the Study of Tobacco Products (CSTP) or Behavioral Health Research Lab (BHRL).
6. * **Describe the process for minimizing coercion to participate:**

Project Coordination

Participant Identification

Participant Recruitment

Participant Consent

Regulatory Management

Other

5. * **The PI certifies that if this individual will conduct any clinical activities as part of this study, the individual is appropriately credentialed and privileged to practice within the institution where the research will be conducted:**

Individual has no clinical responsibilities

6. * **Qualifications to carry out study related responsibilities: (you may select multiple answers)**

Education and/or Professional Preparation

Experience - Research

Experience - Clinical

Experience - Related Skills

Trainee

Student

Other

7. **Additional or Emergency Phone:**

ID: HM20012696

[View: SF_IRB_Summary_Document](#)

Add Document

1. * **Document Name:**
Informed Consent Form

2. * **Type:**
Consent/Assent/Information Sheet

3. * **File:**
[HM20012696 Informed Consent_02.07.2020_CLEAN.pdf\(0.38\)](#) 

ID: HM20012696

[View: SF_IRB_Summary_Document](#)

Add Document

1. * **Document Name:**
CSTP Vaper Advertisements PDF

2. * **Type:**
Recruitment/Advertising

3. * **File:**
[WATT_CSTP_Vaper_Combined_02.07.2020_CLEAN.pdf\(0.08\)](#) 

ID: HM20012696

[View: SF_IRB_Summary_Document](#)

Add Document

1. * **Document Name:**
CSTP Dual Advertisements PDF

2. * **Type:**
Recruitment/Advertising

3. * **File:**
[WATT_CSTP_Dual_combined_02.07.2020_CLEAN.pdf\(0.03\)](#) 

ID: HM20012696

View: SF_IRB_Summary_Document

Add Document

1. * **Document Name:**
Baseline Self Report Physio Measures
2. * **Type:**
Research Measure
3. * **File:**
U54_Baseline forms All_12.18.2019_CLEAN.docx(0.19)  

ID: HM20012696

View: SF_IRB_Summary_Document

Add Document

1. * **Document Name:**
Preession Symptom Questions
2. * **Type:**
Research Measure
3. * **File:**
WATT Preession symptom Checklist-12.18.2019_CLEAN.docx(0.03)  

ID: HM20012696

View: SF_IRB_Summary_Document

Add Document

1. * **Document Name:**
Text, Email, Call Scripts
2. * **Type:**
Other
3. * **File:**
U54_Text, Email, Call, Scripts_11.18.2019_CLEAN.docx(0.11)  

ID: HM20012696

View: SF_IRB_Summary_Document

Add Document

1. * **Document Name:**
Own Brand Questions
2. * **Type:**
Research Measure
3. * **File:**
OB Session Device_E-liquid Questions.9.26.2019_CLEAN.docx(0.03)  

ID: HM20012696

View: SF_IRB_Summary_Document

Add Document

1. * **Document Name:**
BHRL Vaper Advertisements PDF
2. * **Type:**
Recruitment/Advertising
3. * **File:**
These advertisements are no longer used by the study.docx(0.08) 

ID: HM20012696

View: SF_IRB_Summary_Document

Add Document

1. * **Document Name:**
BHRL Dual Advertisements PDF
2. * **Type:**
Recruitment/Advertising
3. * **File:**
These advertisements are no longer used by the study.docx(0.08) 

ID: HM20012696

View: SF_IRB_Summary_Document

Add Document

1. * **Document Name:**
Parking Map
2. * **Type:**
Other
3. * **File:**
CSTP Parking Map .docx(0.01) 

ID: HM20012696

View: SF_IRB_Summary_Document

Add Document

1. * **Document Name:**
Session Drug Purchase Task (PRT)
2. * **Type:**
Research Measure
3. * **File:**
Drug Purchase Tasks_2.19.2019_CLEAN.docx(0.08)  

ID: HM20012696

View: SF_IRB_Summary_Document

Add Document

1. * **Document Name:**
Session Multiple Choice Task (MCP)
2. * **Type:**
Research Measure
3. * **File:**
Multiple Choice Procedure_1.9.2018_CLEAN.docx(0.04)  

ID: HM20012696

View: SF_IRB_Summary_Document

Add Document

1. * **Document Name:**
Baseline Discounting Task
2. * **Type:**
Research Measure
3. * **File:**
Discounting Task_11.7.2018.pdf(0.01) 

ID: HM20012696

View: SF_IRB_Summary_Document

Add Document

1. * **Document Name:**
Baseline Risk taking task - BART
2. * **Type:**
Research Measure

3. * **File:**
[BART_screenshot.11.8.2018.pdf\(0.01\)](#) 

ID: HM20012696

[View: SF_IRB_Summary_Document](#)

Add Document

1. * **Document Name:**
Session subjective measures
2. * **Type:**
Research Measure
3. * **File:**
[Session Subjective Measures 11.9.2018_CLEAN.docx\(0.05\)](#)  

ID: HM20012696

[View: SF_IRB_Summary_Document](#)

Add Document

1. * **Document Name:**
Session Progressive Ratio Task (PRT)
2. * **Type:**
Research Measure
3. * **File:**
[PRT_Version2_10.12.2018.pdf\(0.02\)](#) 

ID: HM20012696

[View: SF_IRB_Summary_Document](#)

Add Document

1. * **Document Name:**
U54 Project 3 Grant Docs
2. * **Type:**
Funding Proposal
3. * **File:**
[U54_Project 3 only docs.pdf\(0.01\)](#) 

ID: HM20012696

[View: SF_IRB_Summary_Document](#)

Add Document

1. * **Document Name:**
BHRL Registry Consent Form
2. * **Type:**
Consent/Assent/Information Sheet
3. * **File:**
[HM20007677 Consent Form_CLEAN_06.22.2017.pdf\(0.01\)](#) 

ID: HM20012696

[View: SF_IRB_Summary_Document](#)

Add Document

1. * **Document Name:**
Criticare HR/BP Manual
2. * **Type:**
Other
3. * **File:**
[Criticare_Vitalcare_506N3_-_Service_manual.pdf\(0.01\)](#) 

ID: HM20012696

[View: SF_IRB_Summary_Document](#)

Add Document

Title: Effects of E-Cigarette Power and Nicotine Content in Dual Users and Vapers

NCT #: NCT03830892

Document date: 01/21/2020

Document Type: Statistical Analysis Plan

Statistical Analysis Plan

Subjective, physiological, DPT, MCP, and PRT data will be prepared as reported elsewhere ([name] et al., 2017; Rusted et al., 1998; [name] et al., 2010). Elasticity is estimated using an exponential demand function with nonsystematic DTP data excluded based on two criteria: trend, or whether the participant had a general decrease in consumption from the lowest to highest price; and bounce, or whether a participant reported higher consumption at sequential higher prices (Stein et al., 2015). In general, analysis will involve a mixed (between- and within-subject) ANOVA. Demographic data will be examined to determine if there are significant between-group differences on measures that may be related to study outcomes (some differences are expected, like cigarette use). Unexpected between group differences will be considered as potential covariates in the primary analysis (see Evans et al., 2006). For all ANOVAs, adjustments for sphericity violations and post-hoc testing using Tukey's HSD or planned contrasts with Bonferroni corrections will be used (Keppel, 1991). Missing data will be imputed using multiple imputation techniques (Allison, 2001).

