4. * Describe the scientific benefit or importance of the knowledge to be gained:

The benefits of this research are of a scientific nature. Specifically, we aim to use study results to inform our understanding of the abuse liability of ECIG device features/characteristics as well as provide information to guide appropriate regulation of ECIGs. We anticipate long term benefits to the public at large by adding to the limited body of knowledge involving these devices among ECIG only users and dual cigarette and ECIG users.

5. * Describe any potential for direct benefits to participants in this study:

None.

6. Upload a supporting citation list if applicable:

ID: HM20012696

View: SF2 - Study Population

Study Population

1. * Provide the maximum number of individuals that

1. May participate in any study interaction or intervention (Including screening, consenting, and study activities)

AND/OR

2. You obtain any data/specimens about (regardless of identifiability)

at VCU and at other sites under the VCU IRB's oversight. See the help text for additional guidance.
300

2. If this is a multi-Center Project, what is the maximum anticipated number of subjects across all sites?

3. * Provide justification for the sample size by explaining how you arrived at the expected number of participants and why this number is adequate for answering the research questions:

120 completers (60 ECIG exclusive users and 60 Dual ECIG and Tobacco Cigarette users) are required to achieve greater than 80% given $p < 0.05$ for the breakpointMCP and breakpointPRT. We excluded own brand controls to ensure we are powered to detect differences across experimental conditions.

We estimate up to 300 individuals may be consented over the course of the study. Please note that initial telephone/web screening is performed under separate protocols - HM20007677 and HM20002567.

4. * List the study inclusion criteria:

General Inclusion:

Age 21 – 55 (verified by photo ID), willing to provide informed consent, they must agree to attend the lab and abstain from tobacco/nicotine as required and able to provide a semi-quantitative urine cotinine result of 'positive' at screening.

ECIG exclusive Inclusion:

Reports using ≥ 1 ml of ECIG liquid/day or approximately one pod/cartomizer per day of at least 3 mg/ml nicotine for the past 3 months or longer and no tobacco cigarette consumption within the past 30 days.

Dual ECIG and Tobacco Cigarette User Inclusion:

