Overview. This study involves 60 current E-Cigarette (ECIG) only users and 60 Dual Users (ECIG + traditional tobacco cigarette) who will complete 5, within-subject, laboratory conditions that differ by the product used: 1) ECIG with low mg/ml; low watts, 2) ECIG with low mg/ml; high watts, 3) ECIG with high mg/ml; low watts, 4) ECIG with high mg/ml; high watts, and 5) own brand (ECIG or tobacco cigarette). The first ECIG 4 conditions will be Latin-square ordered and single blinded such that the participants will not know which condition is administered in each ECIG session. The last condition for all subjects will be their own brand. For ECIG users it will be their own brand ECIG. For Dual Users it will be either own brand ECIG or tobacco cigarette. To allow for comparisons between groups (ECIG vs Dual) for this own brand condition, we will aim for a majority of the Dual User sample to receive their own brand ECIG in the last session.

Participants. A total of 120 adults (ages 21-55) who currently use ECIGs only or dual ECIG and tobacco cigarettes will be enrolled. We will attempt to recruit an equal number of men and women of diverse racial/ethnic backgrounds, although this study is not intended to address gender or race/ethnic differences.

Inclusion criteria: To be included, participants must be healthy, as determined by self-report and heart rate/blood pressure (HR/BP) check, between the ages of 21-55 (as verified by photo ID), and willing to provide informed consent. They must agree to attend the lab and abstain from tobacco/nicotine as required, to use the designated products, and to follow the study protocol.

Participants must also be either A) ECIG only users [reports using ≥ 1 ml of ECIG liquid/day or approximately 1 pod/cartomizer/day of at least 3 mg/ml nicotine for the past 3 months or longer and no tobacco cigarette consumption within the past month] or B) Dual ECIG + traditional tobacco cigarette smokers [reports daily use of ECIG (≥ 3 mg/ml nicotine) or tobacco cigarettes (any frequency) AND some day use (≥ 3 days per week) of ECIGs (≥ 3 mg/ml nicotine) or tobacco cigarettes (any frequency)] use for the past 3 months or longer] who can provide a semi-quantitative urine cotinine result of 'positive' at screening (urine cotinine cassette test).

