Recruitment and Enrollment. Potential participants will be recruited by IRB-approved advertisements, as well as referral from current participants. Once initial screening is completed (either over the phone or via the internet), potentially eligible participants will earn \$10 to come to the lab for in-person informed consent, screening, and familiarization with study procedures (approximately 1.5 hrs). Prior to in-person data collection, staff will review the informed consent with potential participants to ensure they understand the study, its risks and benefits, and their rights as research participants. Following documentation of informed consent, participants will complete baseline measures to confirm eligibility and provide a urine sample that will be tested for cotinine level (to confirm current smoking status) and pregnancy (women only). Age will be verified by asking participants to provide some form of identification that includes a date of birth. We will also take pictures of their device/liquid. All study procedures will be reviewed and participants will be asked to choose the ECIG liquid flavor to be used during the four study ECIG sessions (i.e., not their own brand session). They will be given the opportunity to test four ECIG liquid flavors using the study ECIG device (tobacco, menthol, dessert, fruit) during screening. After flavor testing, participants will complete the Balloon Analogue Risk Task (BART) and the Minute Discounting Task (counter-balanced administration). Depending upon task performance, participants will receive up to \$40 in compensation for the actual amount earned at the end of the BART task.

New recruits will replace participants who do not complete the study. Accrual ends when the required number of completers (N=120) is reached.

Products. Own brand tobacco cigarette packs or ECIG liquids consistent with participant preference will be purchased locally following enrollment. For all other sessions we will provide ECIG liquid at 10mg or 30 mg nicotine and an "open system" ECIG (i.e., Kanger Sub Box Mini C) set to either 15 watts or 30 watts. Liquid flavors available will include tobacco, menthol, dessert, and fruit.

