Procedure. For each session, participants will be asked to refrain from tobacco/nicotine use for ≥ 12 hours and eating food/drinking caffeinated beverages for 1 hour prior to their scheduled session with verification of tobacco/nicotine use status upon arrival at the lab (expired air CO ≤ 7 for ECIG users and ≤ 10 ppm for Dual Users). At the start of the

session, participants rest for 30 minutes, at this time participants will be asked about symptoms experienced since last visit. During this time, participants will not be allowed to use their phones, eat or drink outside beverages but we will provide water to drink and they are invited to read books/magazines or watch movies that we provide to them. Thirty minutes (min) after session onset, participants will sample the session-specific product (2 puffs) followed by a 1 hour rest period, following the same guidelines as the first 30-minute rest period. After the rest period, baseline subjective measures to assess tobacco abstinence symptoms will be completed. Immediately after either the PRT or the DPT/MCP tasks will be completed. The PRT takes approximately 40 minutes to complete and the DPT/MCP takes approximately 40 minutes to complete. Please note that this order, PRT – DPT/MCP or DPT/MCP – PRT, is counterbalanced across participants to control for the effects of completing one task set prior to the other. Following the 1st counterbalanced task assessment, participants will complete a 60-minute rest period. The study procedures should take no more than 240 minutes or 4 hours but study procedures could be completed earlier than that based on decisions the participant makes during the PRT.

0m – CO Check; Physio data collection begins, additional questions about symptoms asked.

30m – 2 puff sample

90m – CO Check; Subjectives measure 1

100m – DPT/MCP OR PRT

140m – Behavioral Measure 1 completed

Subjectives measure 2

Begin 60m rest period

200m – Subjectives measure 3

DPT/MCP OR PRT

240m – Behavioral Measure 2 completed

Subjectives measure 4

end session

Product administration will consist of a 2 sample puff at the beginning of each session. Three behavioral choice tasks will be performed (DPT, MCP, and the PRT). Two of those, (The MCP and the PRT) may yield additional puffs, depending on the decisions made. See the Behavioral Measures section below for more details.

Measures.

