Research personnel are trained to alert the research nurse/medical monitor if heart rate exceeds 120 beats per minute, if systolic BP exceeds 150 mm Hg, or if diastolic BP exceeds 100 mm Hg. Individuals whose heart rate and/or BP levels remain elevated will be monitored continually and if, necessary, emergency responders will be notified. Emergency medical coverage will be available via the emergency room that is 1.5 miles from the CBPL/CSTP or a half block away from the BHRL.

5. * **Describe criteria for when the investigator would withdraw an individual participant from the study; such as safety or toxicity concerns, emotional distress, inability to comply with the protocol, etc.:**
Participants may be withdrawn from the study if the PI/medical monitor/research nurse has any safety concerns (such as observation of high blood pressure; systolic BP ≥ 140 or diastolic BP ≥ 90) during baseline screening or continuous/repeated high blood pressure observations during study sessions.

The PI/research nurse and/or Medical Monitor will be consulted/notified via phone/email specifically concerning high blood observations that occur during any study session to determine whether a participant should remain in the study.

If participants do not comply with study protocol during one of their sessions they may be allowed to repeat that session once.

6. * **Summarize any pre-specified criteria that would trigger the investigator/sponsor/monitoring committee to stop or change the study protocol due to safety concerns:**
We do not have any prespecified criteria for stopping or changing the study protocol due to safety concerns.

Data and Safety Monitoring

Data and safety monitoring is a system for checking the study's data at regular intervals over the study period to identify and address issues that could affect the safety of research participants. This requirement is in accordance with 45 CFR 46.111.

The purpose of data and safety monitoring plan is to set forth study team procedures for monitoring/addressing:

- Participant safety (physical, psychological, etc.)
- Data validity
- Early stopping (termination) based upon changes in risks and benefits.

7. * **Indicate if this study will have a Data Safety Monitoring Board (DSMB) or a Data Safety Monitoring Plan (DSMP): [Required for all greater than minimal risk studies]**

DSMB

DSMP

No DSMB/DSMP [Note: This response is not applicable for greater than minimal risk studies]

Privacy

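### Sessions 1–4 are balanced by Latin square, but the planned mixed ANOVA names no session-position term; adding one, with its interaction with group, is a nearly free gain in precision

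*SAP*

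**What the plan says.** **Design.** Protocol, Study Procedures, item 7 (Overview): "The first ECIG 4 conditions will be Latin-square ordered and single blinded". The participant's own brand always comes last, as session 5. The type of square and the number of sequences are not given.

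**Analysis.** SAP, repeated word for word in the protocol's Data analysis paragraph: "In general, analysis will involve a mixed (between- and within-subject) ANOVA". Sphericity adjustments, Tukey or Bonferroni follow-up and multiple imputation are added. The only covariates foreseen are unexpected differences between the groups. No session, period, sequence or order term appears, and group, nicotine and power are not named as model terms either.

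**Sizing.** Study Population, item 3 asks for 120 completers (60 per group) for power above 80% at p < 0.05 on the two breakpoint outcomes, and adds: "We excluded own brand controls to ensure we are powered to detect differences across experimental conditions".

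**Provisions that affect balance.** Recruitment and Enrollment: "New recruits will replace participants who do not complete the study". The sequence that a replacement receives is not stated. Risks, Discomforts, Potential Harms and Monitoring, item 5: "If participants do not comply with study protocol during one of their sessions they may be allowed to repeat that session once".

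**The concern.** A Latin square makes session position a controlled factor. The benefit is fully realised only if the analysis also removes position. If participants change over the four visits, through practice on the tasks, familiarity with the device or fatigue, and the model holds only group, nicotine and power, that change is left in the residual. The affected tests then use an error term that is too large.

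Any loss would fall on the contrasts the trial was sized for, namely the differences across experimental conditions. The group-by-condition contrasts share the same error, and they carry the hypothesis that exclusive users respond more strongly to lower nicotine. Leaving the term unnamed also means that it could be added or dropped after the data are seen.

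**Working it through.** **The plan's own figure.** Power above 80% cannot be reproduced, because no effect size, SD, within-person correlation or tested effect is given. Solving backwards at two-sided 0.05 (sidedness assumed), 120 completers have 80% power for a within-person contrast of 0.258 SD and 90% power for 0.298 SD. These serve as reference effects.

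**Inputs from the documents.** Four experimental conditions in a Latin square; 60 + 60 completers; alpha 0.05.

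**Assumptions.** Within-person SD = 1 with normal, equal-variance errors. Four sequences, so 60/4 = 15 per sequence per group. Linear drift common to everyone, D(p−1)/3 at position p = 1..4, so D is the total drift from session 1 to session 4.

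**Step 1: does drift bias the contrasts?** Take the orthonormal nicotine, power and interaction contrasts and compute what drift adds to each, by sequence, for D = 1.

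- Carryover-balanced square: one contrast gets 0.667, 0.333, −0.667, −0.333; another gets −0.333, 0.667, 0.333, −0.667; the third gets 0 throughout.
- Cyclic square: two contrasts get 0.667, 0, −0.667, 0 (in some order); the third gets 0.333, −0.333, 0.333, −0.333.

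Each set averages to zero, so there is no bias under balance. Which contrast falls where depends on how conditions are assigned to the letters of the square.

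**Step 2: what goes into the error?** The mean square of each set is the added variance V.

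- Carryover-balanced: (4/9 + 1/9 + 4/9 + 1/9)/4 = 5/18, so V = 5D²/18 for two contrasts and 0 for the third.
- Cyclic: (4/9 + 0 + 4/9 + 0)/4 = 2/9 for two contrasts; (4 × 1/9)/4 = 1/9 for the third.

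Both squares average (1/3) × 5/9 = 5/27, so a pooled error is inflated by the factor 1 + 0.185D².

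**Step 3: power without a position term.** Under balance the contrast mean keeps variance 1/120. The error mean square on 118 df follows a scaled noncentral chi-square with noncentrality 120V. Power in %, for a contrast of 0.258 SD:

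| D (SD) | V = D²/9 | V = 2D²/9 | V = 5D²/18 |
|---|---|---|---|
| 0 | 80.0 | 80.0 | 80.0 |
| 0.258 | 79.8 | 79.6 | 79.5 |
| 0.5 | 79.2 | 78.4 | 78.0 |
| 1.0 | 76.8 | 73.6 | 71.9 |

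True two-sided error at nominal 5%, in the same column order, is 4.69, 4.40 and 4.27% at D = 0.5, and 3.88, 3.02 and 2.67% at D = 1.0. The tests are conservative. From a 90% base, D = 1.0 leaves 88.0, 85.8 and 84.6%. With a pooled error, the large-sample figure at D = 1.0 is 74.8%, inside the range above.

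**Step 4: power with position fitted.** In simulation (4,000 trials per setting, D = 1.0), power returns to 79–81%. With no drift, the cost on sequence-adjusted contrast scores is 118 to 115 df, which moves power from 80.00% to 79.98%. Adding group-by-position (112 df, same formula) gives 79.97%.

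**Step 5: drift that differs by group.** Let D = 1.0 in one group only.

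- No position term: noncentrality 60V, power 76.0–78.4%.
- Common position term only: it removes the average and leaves ±0.5 SD in the two groups, so noncentrality is 30V and power 78.0–79.2%. Part of the loss remains.
- Opposite drifts of equal size: a common term recovers nothing.

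Group-by-position removes the group-specific part in each case.

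**The case against.** **The harm is conditional and small.** There is no bias under balance, and the tests err on the safe side. Drift equal to the whole detectable effect costs at most about 0.5 points. The 3–8 point loss needs drift about four times that effect (1.0/0.258 ≈ 3.9). The design also works against large drift. Participants try the device at screening ("They will be given the opportunity to test four ECIG liquid flavors using the study ECIG device"), and every session repeats the abstinence, rest and two-puff sample. All of this stands and sets the severity low.

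**The SAP does not exclude a position term.** It says only what the analysis will involve in general, and it leaves every model factor unnamed. That is right: this is a gap in specification, not a stated omission. The gap can still be closed at almost no cost.

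**The decimals are exact only under the assumed model.** Breakpoints are discrete and may be skewed or capped: the progressive-ratio requirement doubles with each puff, and the multiple-choice form has 15 rows. The figures show order of magnitude only.

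**Neighbouring issues do not enlarge the point.** Task order within a session "is counterbalanced across participants to control for the effects of completing one task set prior to the other", and its main effect does not bear on the condition contrasts. Own brand is always session 5, so comparing it with the study conditions is confounded with position, but it lies outside the sizing. The own-brand comparison the protocol does announce is between groups ("To allow for comparisons between groups (ECIG vs Dual) for this own brand condition"), and position is the same for both.

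**Conclusion.** The point holds as a low-severity, nearly free improvement. Without a position term, shared drift enters the error of most condition contrasts: all three in a cyclic square, two of three in a carryover-balanced one. From an assumed 80% base, the loss is at most about 0.5 points at 0.26 SD of drift, 1–2 points at 0.5 SD and 3–8 points at 1.0 SD. This rests on linear shared drift, four exactly balanced sequences and normal errors.

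A reader might infer more than the documents support:

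- **That the nicotine and power estimates are biased.** With balanced sequences they are not. Drift would leak into the contrasts only if replacements or repeated sessions upset the balance, and nothing shows that it will be upset.
- **That the trial is underpowered.** The protocol claims power above 80% without an effect size or SD, and no drift is documented. From a 90% base, even 1.0 SD of drift leaves at least 84.6%.
- **That a position term cures any drift.** A common term removes only the shared part. Group-by-position also removes drift that differs by group. Drift peculiar to individuals stays in the error.

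**What to change.** In the primary analysis of the four experimental conditions, state that the model includes:

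- group, nicotine, power and their interactions;
- session position (1–4) as a fixed effect, with group-by-position;
- participant as a random effect in a linear mixed model, or the equivalent Latin-square ANOVA.

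Each participant meets each condition in one position only, so position cannot simply be entered as another crossed within-subject factor in a standard repeated-measures layout.

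Define whether position means the scheduled slot or the actual visit order when a session is repeated. Have each replacement take the vacated sequence within the same group, and report completers per sequence by group so that balance can be seen.

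**Cost.** SAP wording and one scheduling rule, with no new data. Position uses 3 degrees of freedom and group-by-position 3 more. With no drift, power falls by about 0.02 points for position alone and about 0.03 in all (80.00% to 79.97%).
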